#### JHM IRB - eForm A - Protocol

- Use the section headings to write the JHM IRB eForm A, inserting the appropriate material in each. If a section is not applicable, leave heading in and insert N/A.
- When submitting JHM IRB eForm A (new or revised), enter the date submitted to the field at the top of JHM IRB eForm A.

\*

#### 1. Abstract

Intimate partner violence disproportionately affects immigrant women. However, immigrant women remain an understudied and underserved population in need of evidence-based rigorously evaluated culturally competent interventions that address their health and safety needs. This study uses a sequential, multiple assignment, randomized trial design to rigorously evaluate an adaptive culturally informed intervention tailored to the needs of immigrant women with intimate partner violence (IPV) experiences. For the first stage randomization, the abused immigrant women are being randomized to the It's weWomen Plus online intervention or the usual care control arm and safety, mental health and empowerment outcomes are assessed at 3, 6 and 12 month follow up. In this study, women who do not report significant improvement in safety (i.e., reduction in frequency and severity of intimate partner violence) and in empowerment from baseline to 3 months (i.e., non-responders) will be re-randomized to a second stage randomization with augmented intervention components (i.e., text messages and phone calls).

In Phase 1, the formative phase, using a concurrent mixed methods design, we will conduct in-depth interviews with non-weWomen participants and current weWomen (1R01HD08117901A1) participants. The participants will be asked about the utility of the It's weWomen Plus intervention components. We will also analyze moderators of intervention response. Further, based on input from experts on IPV among immigrant women and from diverse groups of immigrant survivors of IPV, we will culturally tailor and pre-test the content of the augmented components (text messages and phone calls' protocol) (qualitative).

Also as part of Phase 1, we will conduct a pilot test of the present study's intervention components with 5 to 10 immigrant survivors of IPV to ensure that the registration process, surveys, online intervention, text message intervention, and phone intervention work as intended and to identify any technology issues in our intervention. The eligibility criteria of survivors will be the same as the Phase 1 in-depth interview participants.

In Phase 2 (Enhanced intervention evaluation) phase, by re-randomizing participants, we will assess the relative effectiveness of two strategies for augmenting the It's weWomen Plus online intervention (text messaging only or a combination of text and phone) on safety and empowerment outcomes among the non-responders of the It's weWomen Plus online intervention. In addition, the study will compare the non-responder group of women to the responder group of the It's weWomen Plus online intervention to determine if the strategies of augmentation brought the non-responders to the level of responders on safety and empowerment. Furthermore, a subsample of 55 women with abuser's access/ownership of guns will be receive a gun safety intervention and their outcomes will be compared with 55 women with abuser's access/ownership of guns in the control arm who did not receive the gun safety intervention.

In Phase 3 (Dissemination and Implementation) phase, the study will identify facilitators and barriers to the adoption, implementation and maintenance of use of the original and augmented intervention by programs serving immigrant women and design strategies to decrease barriers and build on strengths. For this, the study will collect data from providers serving immigrants and organizational leaders as well as immigrant survivors of intimate partner violence (those who received the It's weWomen Plus online intervention only as well as those who received the augmented intervention components). The intervention will result in an evidence-based culturally informed intervention for immigrant survivors of IPV for use by practitioners serving immigrant women.

## Phase 1 AIM 1 (Formative)

- a) To identify and understand factors related to response or non-response to the It's weWomen Plus intervention
- b) To culturally tailor and pre-test the content of the new enhanced support components (text messaging and phone) for It's weWomen Plus intervention with a diverse group of immigrant women.

## Phase 2 AIM 2 (Enhanced Intervention Evaluation)

- a) To assess the relative effectiveness of two strategies for augmenting the It's weWomen Plus intervention (text messaging only or a combination of text and phone) on safety, mental health and empowerment outcomes among the non-responders.
- b) To compare the non-responder group of women to the responder group to determine if the strategies of augmentation brought the non-responders to the level of the responders on safety, mental health and empowerment
- c) To pilot test a gun safety intervention with a sub-sample of 55women who reported partner's ownership or access to a gun and compare their outcomes to 55 women who reported partner's ownership or access to a gun who did not receive the gun safety intervention

#### Phase 3 AIM 3 (Dissemination and Implementation)

To identify facilitators and barriers to the adoption, implementation and maintenance of use of the original and augmented intervention by programs serving immigrant women and to design strategies to decrease barriers and build on strengths

#### 3. Background

Foreign-born immigrant women are at high risk of IPV and intimate partner homicide (IPH). Prevalence rates of IPV in community-based studies of immigrant women range from 24% to 60%. However, there are no rigorously evaluated interventions for abused immigrant women, who most likely remain at high risk of revictimization and negative effects of IPV and are underserved. The It's weWomen Plus online intervention (i.e., myPlan intervention culturally adapted for immigrant women via input from immigrant survivors of IPV and from practitioners serving immigrant women) uses the web-based platform to assess women's level of danger for severe IPV/IPH in abusive relationships using the Danger Assessment (DA). The DA assesses level of danger in relationships using 20 yes/no questions about risk factors (e.g., increase in frequency and severity of violence). A weighted scoring system identifies women at the following levels of danger: variable

(<8), increased (8-13), severe (14-17) and extreme (≥18) danger. Women receive immediate graphic feedback on the DA score with level of danger and evidence-based messages to inform interpretation of the danger level and taken through a priority-setting activity where they can consider values (e.g. privacy, feelings for partner, having resources, safety and well-being of children) with regard to relationships. Information provided by the users, (such as relationship status) and the DA score are combined with the safety priorities of the users to develop a tailored safety action plan with links to resources and services. However, due to the varying needs of immigrant women, all immigrant women may not experience improvement in outcomes via intervention at the same intensity level. Immigrant women unable to implement a safety plan on their own using an online app may benefit from additional support via phone and/or text focusing on other strategies to increase support from other immigrant women and specific strategies aimed at their abusive partners building further on the knowledge gained in the formative phase of It's weWomen Plus.

#### 4. Study Procedures

a. Study design, including the sequence and timing of study procedures

The study will use a mixed methods design and will be conducted in three phases: Formative (phase 1), Enhanced Intervention Evaluation (phase 2) and Dissemination and Implementation (phase 3).

- a) For formative phase (Phase 1), the study will use a concurrent triangulation mixed methods design that includes:
  - (i) 45-50 in-depth, semi-structured interviews that explore the perceptions of newly recruited immigrant women as well as current weWomen participants. The newly recruited participants and any participants from the weWomen study with whom we conduct in-depth interviews will be asked about the utility of online intervention components and also provide feedback on phone and text intervention components. We have added the newly recruited women to the in-depth interview portion of Phase 1 since we have very few participants from the weWomen study who completed 12 months of follow up. Additionally, not all women from the weWomen study agreed to be contacted for future studies. The inclusion criteria for newly recruited nonweWomen participants will be the same as weWomen participants. The nonweWomen participants who participate in the in-depth interviews will be compensated the same amount as the participants in the in-depth interviews who completed weWomen. To achieve maximum variation in country of origin/ethnicity, participants from various regions (e.g., Latin America, Asia, and Africa) will be purposefully recruited for the in-depth, semi-structured interviews. The follow-up interviews for current participants in the ongoing weWomen study will take place only for those women who complete 12 months assessments and agreed to be contacted for follow up interviews. Trained research assistants will conduct these interviews by phone or in person (depending on the participant's location and preference).
  - (ii) In addition input will be obtained from 15-30 experts on IPV in immigrant women from multiple disciplines and from diverse groups of 30 immigrant survivors of IPV not part of the weWomen RCT via 5 focus groups (4-8 immigrant women/group) to further develop and culturally tailor the added text messaging and phone components to the It's weWomen Plus intervention. The input from cultural experts will be obtained over the phone, in-person or via email depending on their preference. The

Date: January 2nd, 2025

check ins will only occur in months where participants have no contact with the team for text and/or phone intervention sessions. These include months 1, 2, 5, 7, 8, 9, 10, and 11 of the weWomen Plus study. We are engaging in retention messaging in an effort to promote participant engagement since we experienced poor retention in the prior WeWomen study.

- ii) We will conduct 20-30 semi-structured post-12 month follow up interviews with women who received the gun safety intervention and agreed to be contacted for the interview. The interview guide will be developed to obtain feedback on their experience and how to further refine the intervention for future large scale trial. We will pay each woman \$35 for participating in the interview.
- c) For dissemination and implementation (Phase 3), the study will use a qualitative design. This phase involves purposefully sampling providers from a range of different types of organizations that serve immigrant women, including those that have an explicit violence response mission and those which do not. It will also seek maximum variation in organizational size, geographic location, and population of immigrant women served. The plan is to interview 25-30 providers from immigrant focused organizations (in each case, to be comprised of 12-15 providers from IPV focused organizations and 12-15 from non-IPV focused organizations). In addition to the 25-30 providers, 25-30 organizational leaders from both types of organizations will be interviewed. To be eligible for participation, the providers or organizational leaders must have extensive experience (two or more years) providing services to immigrant survivors of IPV. Further 25-30 immigrant survivors of IPV from Phase 1 and/or Phase 2 will be interviewed to follow up on emergent themes related to implementation developed during Phase 1 and Phase 2 analyses. This will include those who received the augmented components (n=22-25) as well as those who just received the It's weWomen Plus online intervention alone (n=12-15). These interviews will be done after completing Phases 1 and 2 and in the final years of the study. The interviews will last for approximately one hour to two hours, depending on the information shared by participants.

intervention website or the control website. The intervention group will receive the It's weWomen Plus online intervention. The control group will receive non-DA informed usual safety planning resources modeled on national and state DV online resources. In the second stage re-randomization, non-responder participants will be re-randomized to additional text-only or text messaging and phone intervention. Participants will not be informed about their assignments to the intervention content or the control content. It is anticipated by this process, any differences in safety, mental health and empowerment outcomes can then be linked to the internet/and or accessible intervention and not to the participants' knowledge of the new intervention or expectations that the safety planning informed by the DA is better than the usual non-DA informed safety planning.

d. Justification of why participants will not receive routine care or will have current therapy stopped.

Not applicable (N/A)

e. Justification for inclusion of a placebo or non-treatment group.  $\ensuremath{N/A}$ 

Once a participant finishes the survey referenced in the above email, the participant will receive the following email that will give them access to the online resource (referred to as "Part 2" in the email):

#### Hello [PARTICIPANT NAME],

Thank you for completing the survey! We know it was long, and we really appreciate you taking the time to fill everything out. When you're ready to start Part 2, click on the link below. We'll send you your incentive once you've gone through Part 2.

#### 5. Inclusion/Exclusion Criteria

## For Phase 1 (Formative Research):

a) to identify and understand factors related to response/non-response to the It's weWomen Plus intervention,

The following inclusion criteria will be used to select women for in-depth interviews:

- Over 18 years of age
- Foreign born immigrant background
- Have experienced IPV within the past year
- b) to culturally-tailor and pre-test the content of the new enhanced support components (text messaging and phone calls) for the It's weWomen Plus intervention with a diverse group of immigrant women,

The inclusion criteria for experts will be:

- Two or more years of experience serving immigrant survivors of IPV, and
- Psychology, social work, public health or nursing background. OR
- Expertise in any discipline, and
- Served survivors of IPV for 10 years or more

The inclusion criteria for women will be

- Not a current participant in the WeWomen RCT;
- over 18 years of age,
- Foreign-born immigrant woman from Africa, Asia or Latin America, and
- have experienced IPV within the past year.

#### For Phase 3 (Dissemination and Implementation)

The eligibility criteria for providers and organizational leaders will be:

• Two or more years of experience providing services to immigrant survivors of IPV.

The eligibility criteria for women will be:

- Participated in Phase 1 and/or Phase 2 interviews and/or focus groups;
- over 18 years of age,
- Foreign-born immigrant woman from Africa, Asia or Latin America, and
- Survivor of IPV.

## 6. Drugs/ Substances/ Devices

N/A

## 7. Study Statistics

#### a. Primary outcome variable:

 Safety: Change in severity and frequency of physical violence from baseline to followup)

#### b. Secondary outcome variables:

- Mental Health: Change in PTSD and/or depression symptoms from baseline to follow-up
- Empowerment (Overall empowerment and empowerment related to safety): Change in empowerment scores from baseline to follow-up

#### c. Statistical plan including sample size justification and interim data analysis.

Based on results from our prior Risk Assessment Validation Study, we expect 30% of women to be non-responders (e.g., increase in severity and frequency of IPV) in the It's weWomen Plus intervention arm. Assuming an 80% retention rate at 12 months, we determined the sample per group needed to detect an effect is of .25 or greater. The addition of the phone component will focus on multiple issues using evidence-based approaches to interaction whereas the text messaging is tailored to the safety plan only. The phone-based intervention will allow more rapport building and personalized care via interaction with a trained interventionist using strengths-based approaches, so we expect an effect size in the small to moderate range (Cohen's d' of .2-.4). Interventions drawing from SMART design/SMART interventions may be powered similar to a standard RCT, if stage-specific questions (e.g., a comparison of first-stage interventions averaging over response and second stage interventions) are of primary interest and embedded dynamic treatment regimen development is of secondary interest. With power = 0.80, alpha = 0.05, and N=253 per group, we will be able to detect significant differences in the change over time between the two groups when the effect size is 0.25 or greater. This will require a total sample size of N=1,266 with 633 randomized to the It's weWomen Plus

intervention and 633 to usual care. With a 30% nonresponse rate, 190 women will be eligible to be randomized to It's weWomen Plus online intervention+text messaging or the It's weWomen Plus online intervention+ text messaging + phone contact with 95 per group. We expect a higher rate of non-responders in the control arm, with 50% of women (N=316) eligible for randomization into groups ( the It's weWomen Plus online intervention +Text Messages or the It's weWomen Plus online intervention + Text Messages +Phone Calls) with N=158 per group. Using the eligibility criteria of women aged 18 or older, foreign-born Latina, Asian or African, have experienced IPV in the past year, and have access to a safe computer/smartphone and are comfortable using it to access the study, we will recruit 1,266 women for the proposed study. In addition, we will recruit 55 women with abuser's access/ownership of firearm for pilot test of the gun safety booster intervention and compare it with 55 women with abuser's access/ownership of firearm in the main trial usual care control arm.

To identify and understand factors related to response/non-response to the It's weWomen Plus intervention will be tested among those randomly assigned to the It's weWomen Plus intervention group. Logistic regression will be used to identify baseline variables related to response/non-response. We will examine 2 indicators of response (safety and empowerment). For safety, non-response will be defined as no change or an increase in severity and frequency of IPV at follow-up; for empowerment non-response will be defined as no improvement in empowerment scores (at least a 0.25 standard deviation increase in scores) from baseline to follow up. Predictors of response will include demographic factors of age, race, marital status, and time in the US; risk factors (i.e., attitudes towards violence against women, discrimination, previous experience of IPV), and social support. Results from these analyses will be triangulated with results for the qualitative analyses to identify key factors for tailoring in future implementation of the intervention. To assess the relative effectiveness of two strategies for augmenting the It's weWomen Plus online intervention on safety, mental health and empowerment outcomes among the non-responders, Generalized Estimating Equations (GEE) with robust variance estimation will be used. Variables in the model include time (baseline and 12 months) and group which will have two levels: It's weWomen Plus online intervention and the addition of text messaging and It's weWomen Plus online intervention and text messaging and phone contact. Baseline variables on which the groups are not balanced by randomization will be included as covariates. The parameter of interest is the group by time interaction which will determine if the change over time in the outcome variables differs between the two groups. We will conduct sensitivity analyses including baseline variables found to predict intervention response and dose of the initial intervention. Dose will be captured by the number and duration of prescribed sessions/timepoints of intervention completed, number of and duration of unprescribed sessions (i.e., woman visiting intervention website outside the prescribed time points) and receipt of usual care services. These variables will be added to the GEE models described above to determine if significant differences in change over time remain controlling for predictors of non-response and dose of the initial intervention. Similarly, to determine if the strategies of augmentation brought the non-responders to the level of the responders on outcomes, GEE also will be used controlling for baseline variables on which the groups are not balanced by randomization. In this analysis there will be four groups: responders to usual care control arm and responders to the It's weWomen Plus online intervention, the It's weWomen Plus online intervention and the addition of text messaging and the It's weWomen Plus online intervention and text messaging and phone contact. Responders will be coded as the reference group in order to compare responders to the two groups of non-responders that received augmentation. Once again, the group by time interaction will be the parameter of interest to determine if the change over time in the outcomes differs between the responders and those receiving either adaptive intervention. We will use the 'weighted and replicated' estimation

method that effects for the adaptive interventions can be simultaneously estimated in the same model. Inverse probability weighting for probability of receiving an adaptive intervention will be relative to the number of times an individual is randomized (e.g. responders have a weight of ½ and non-responders have a weight of ½). As observations need to be used in more than one comparison, data will be replicated. Sensitivity analyses will include dose of initial intervention (as described above) and baseline variables found to predict intervention response in Phase 1 as covariates in the models.

Potential Confounding Variables. T-test and chi-square tests will be used to examine if each randomization succeeded in creating balance on key demographic and baseline outcome variables. We will control for any variables that are found to be significantly different in the corresponding main analyses.

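### Baseline covariates entered as main effects do little or nothing to adjust the group-by-time parameter, so the planned imbalance control and sensitivity analyses are largely uninformative for it

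*Combined protocol and SAP*

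**What the plan says.** All the relevant text is in section 7c (statistical plan) of the combined protocol and SAP.

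- **Model for Aim 2a.** "Generalized Estimating Equations (GEE) with robust variance estimation will be used", with time at two levels (baseline and 12 months) and group at two levels (text, or text plus phone).
- **Adjustment and test.** Baseline variables on which the groups differ "will be included as covariates. The parameter of interest is the group by time interaction". The Potential Confounding Variables paragraph says these variables are found by t-tests and chi-square tests.
- **Sensitivity analyses.** For predictors of response and dose of the initial intervention: "These variables will be added to the GEE models described above to determine if significant differences in change over time remain".
- **Aim 2b.** Responders and augmented non-responders are compared in the same kind of model, again on group by time. The sensitivity analyses add dose and "baseline variables found to predict intervention response in Phase 1 as covariates in the models".

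No sentence gives a covariate-by-time term or a baseline-adjusted 12-month model. The link, the working correlation and the handling of missing 12-month data are not stated either.

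**The concern.** The natural reading of the text is that covariates enter as main effects. A main effect adjusts the level of the outcome, but the plan tests the difference in change. A covariate that affects how much a woman changes can only be adjusted for through its interaction with time.

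Three things are at stake. A chance imbalance that the plan undertakes to control would stay in the Aim 2a estimate. Agreement between main and sensitivity analyses could be reported as robustness although it follows largely from the form of the model. In Aim 2b the groups are formed by outcome, and the plan deliberately looks for variables that predict response. Such variables are candidates to affect change, yet they would not be adjusted for in the parameter tested.

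**Working it through.** **Inputs from section 7c.** Two time points, two groups, test on group by time; "With power = 0.80, alpha = 0.05, and N=253 per group"; effect size 0.25 in change over time; "Assuming an 80% retention rate at 12 months". Sidedness is not stated, and I assume two-sided tests at 0.05.

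**The plan's own figure.** n = 2(1.960 + 0.842)² / 0.25² = 2 × 7.85 / 0.0625 = 251.2, so 252 per group against 253 stated. Power with 253 is 0.803. The figure reproduces, and 253 = 95 + 158, the two re-randomised strata.

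**Algebra.** Let t be 0 at baseline and 1 at 12 months, g the group and x a covariate with one value per woman.

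- As written: E(Y) = β0 + β1·g + β2·t + β3·g·t + γ·x. The expected change is β2 + β3·g, and γ·x has cancelled.
- With covariate by time: add δ·x·t. The expected change is β2 + β3·g + δ·x.
- Leaving out δ biases β3 by δ × (difference in mean x between groups).

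With complete pairs, an identity link and an independence or exchangeable working correlation, the estimating equations separate into one for each woman's sum and one for her difference. The covariate enters only the sum. Under a log link, γ·x multiplies both means by the same factor and leaves their ratio alone.

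**Numerical check.** Simulated GEE fits with robust SE, 253 per group, true group-by-time effect −0.25, 15 data sets per setting. Two values are assumed and not from the documents: a covariate imbalance of 0.3 SD and a covariate effect on change of 0.4 per SD. The expected bias is 0.3 × 0.4 = 0.12. Mean estimates under the identity link:

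| Data | Working correlation | No covariate | Main effect | Covariate by time |
|---|---|---|---|---|
| Complete | Independence | −0.129 | −0.129 | −0.251 |
| Complete | Exchangeable | −0.109 | −0.109 | −0.216 |
| 20% lost at random | Independence | −0.145 | −0.138 | −0.256 |
| 20% lost at random | Exchangeable | −0.106 | −0.106 | −0.228 |
| Loss tied to covariate, opposite directions by group | Independence | −0.386 | −0.195 | −0.245 |
| Loss tied to covariate, opposite directions by group | Exchangeable | −0.333 | −0.249 | −0.259 |

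With complete data, adding the main effect changed the estimate by 0.00000 and left the SE ratio at 1.0000. Covariate by time made the SE about 6% smaller. A log link with complete data also gave no shift. A logit link gave a shift of about 0.1 SE with an SE about 10% larger, which reflects non-collapsibility and is not a correction. Under random loss the shift was 0.08 to 0.32 SE, depending on the covariates added and the working correlation. A further check under 20% random loss gave 0.144 without the covariate, 0.144 with its main effect and −0.001 with covariate by time.

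**Size in Aim 2a.** The SE of a standardised imbalance is √(2/253) = 0.089. A t-test at 0.05 therefore flags imbalances above about 1.96 × 0.089 = 0.174 SD. The uncorrected bias at that trigger is slope × 0.174:

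- slope 0.5 per SD: 0.087, or 0.087/0.25 = 35% of the design effect;
- slope 0.2 per SD: 0.035, or 14%.

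**Size in Aim 2b.** Larger imbalances are plausible because the groups are not randomised. At an assumed 0.3 SD the bias is 0.06 (slope 0.2) to 0.15 (slope 0.5).

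**Which regression matches.** With a baseline difference of 0.5 between non-randomised groups and no difference in change, covariate-adjusted change gave −0.01. The 12-month score on group and covariate gave 0.49, and adding the baseline score gave 0.24. Only the first matches covariate by time.

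**The case against.** The strongest reply is that the text under-specifies the model and contains no stated error: nothing in section 7c excludes time interactions. That is fair, but main effects are what a programmer would fit from the wording, so the plan needs to say otherwise.

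Four stronger readings are tempting, and the documents do not support them.

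- **Adjusted and unadjusted results will be identical.** A reader might infer this, but it is exact only for women with both time points under an identity or log link. The plan expects 20% loss and names no link. If loss depends on the covariate differently by group, the main effect moves the estimate materially (0.8 to 1.7 SE above) and then does some work against differential dropout. Dose could also be coded by time point, for example zero at baseline, and would then not cancel.
- **Aim 2a has an inflated false-positive rate.** Fixing a 0.3 SD imbalance in every run, with slope 0.5 and 20% loss, gives 33% rejections unadjusted, 34% with the main effect and 4% with covariate by time. Under randomisation, though, 0.3 SD is 0.3/0.089 = 3.4 SE (two-sided p = 0.0007 per covariate). With imbalance left to chance, the same slope and complete data, 4,000 runs gave 4.5% unadjusted and 4.7% adjusted.
- **Aim 2b has no confounding control.** Group by time already removes stable differences in level. What is missing is adjustment for measured covariates that affect change.
- **Covariate by time makes Aim 2b sound.** Section 4a defines responders by their own change from baseline to 3 months, which is part of the change to 12 months. No baseline covariate term removes that selection.

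**Conclusion.** The point holds in a limited form. As naturally read, section 7c adjusts a parameter it does not test. For women with both time points under an identity or log link, the group-by-time estimate is the same with or without a time-constant main effect. Under 20% random loss it can move slightly, but the bias is essentially uncorrected. The sensitivity analyses are therefore largely uninformative about whether a difference in change survives adjustment.

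In Aim 2a the cost is conditional bias after an unlucky allocation, about 0.09 at the trigger if the slope is 0.5 per SD and less for smaller slopes, plus some precision. Validity on average is not in question. Aim 2b is where the point matters most, because no randomisation stands behind the comparison and the stated weights reflect only the number of randomisations. The cancellation is algebra. The sizes rest on assumed slopes and imbalances that the documents do not give.

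**What to change.** In section 7c, in the paragraphs on both aims and on the sensitivity analyses, state that each time-constant covariate enters with its covariate-by-time interaction. This covers imbalanced baseline variables, predictors of response, and dose if coded once per woman. For complete data and an identity link, this equals regressing change on group and covariates. State the link, the working correlation and how dose is coded.

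For the randomised Aim 2a comparison only, a 12-month model adjusted for the baseline outcome and covariates is a valid alternative. It is a different estimator and should be labelled so. It should not be used for Aim 2b, where it can turn a baseline difference into an apparent effect.

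For Aim 2b, add a sentence that covariate by time adjusts only measured covariates and does not remove selection from defining responders by their own 3-month change.

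The cost is a few sentences and one extra term per covariate (more for a categorical covariate), with no new data. It should be settled before outcomes are analysed.
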